12.1.3 MALARIA CHALLENGE AGENT ADMINISTRATION (DAY 0)

Participants, including up to three reserve participants per inoculation day, will report to the clinical trial unit on the morning of the day of inoculation. The Investigator will review the participants' screening and eligibility confirmation visit results prior to their inoculation.

On arrival to the clinical trial unit, participants will be required to undertake further procedures to determine whether they remain eligible. A reserve participant may be asked to replace a participant who does not meet eligibility. The reserve participants will be compensated for the study visit even if not inoculated, as described in the Participant Information Sheet and Consent Form.

The procedures that will be undertaken prior to inoculation include:

- Verify that all applicable eligibility criteria have been met.
- Elicit information regarding any new medical conditions, illnesses and medication use since screening visit.
- Perform COVID-19 rapid test.
- Perform alcohol breath test.
- Perform urine drug screen.
- Perform urine β -hCG pregnancy test for WOCBP.
- Perform abbreviated physical examination.
- Record vital signs.
- Obtain a 12-lead ECG in triplicate.
- Obtain malaria clinical score.
- Cannulate participants with an indwelling intravenous cannula (20 or 22 gauge) for the malaria challenge agent, and record which arm is utilised.
- Collect blood samples for:
 - malaria PCR (baseline sample),
 - safety serum retention sample,
 - Future malaria research sample (if participant has consented).

Administration of the malaria challenge agent:

- Administer the malaria challenge agent of ~2,800 viable *P. falciparum* 3D7 infected human erythrocytes intravenously.
- Observe for a minimum of 60 minutes after inoculation to evaluate for immediate adverse reactions.
- Educate participants on signs and symptoms of malaria.
 - a. Signs of malaria include fever (oral temperature above 38°C), chills/shivering/rigors, tachycardia, hypotension.

- b. Symptoms of malaria include headache, myalgia, arthralgia, fatigue/lethargy, malaise, sweating/hot spells, loss of appetite, nausea, vomiting and abdominal discomfort.
- Provide participants with diary cards and thermometers to record any temperature readings during the study in the event of symptoms of fever. Participants will also record symptoms, details of self-administered take home definitive antimalarial medication and concomitant medications on the diary cards during the study.
- Record AEs and concomitant medications.
- Record vital signs prior to leaving the clinical trial unit (approximately 60 minutes after inoculation).

12.1.4 OUTPATIENT MONITORING PRE-IMP ADMINISTRATION (DAY 1 TO DAY 7AM)

Monitoring via phone (Days 1 to 3):

During this period, the participants are expected to be asymptomatic. A daily phone call or text message will be made to the participant by clinical trial unit staff to monitor participant well-being and to solicit any AEs and concomitant medications. Participants will be reminded to fill in their diary cards.

Daily visits to the clinical trial unit for monitoring (Days 4 to 7):

Follow-up from Day 4 to Day 7AM will be undertaken through daily morning visits to the clinical trial unit.

The following procedures will occur during these visits:

- Perform symptom-directed physical examination if clinically indicated.
- Record vital signs.
- Obtain malaria clinical score.
- Collect blood sample for malaria PCR.
- Collect sample for COVID-19 PCR test (Day 6AM).
- Collect blood samples for haematology and biochemistry (Day 7AM).
- Record AEs and use of concomitant medications.
- Check participant diary cards.

12.1.5 INPATIENT OBSERVATION AND IMP ADMINISTRATION (DAY 7PM TO DAY 11)

Participants will be admitted to the clinical trial unit on Day 7PM, in preparation for single-dose administration of MMV367 on Day 8 when parasitaemia for the majority of participants is expected to be above 5,000 parasites/mL. Participants will be provided with a light snack the evening prior to dosing and then fast from all food and drink (except water) for a minimum of 8 h on the day prior to dosing until approximately 4 h post-dose, at which time lunch will be provided.

The following procedures will occur on admission to the clinical trial unit Day 7PM:

- Alcohol breath test.
- Urine drug screen.
- Urine β -hCG pregnancy test for WOCBP.
- Perform COVID-19 rapid test.

The following procedures will occur pre MMV367 administration on Day 8:

- Perform abbreviated physical examination.
- Obtain and review a 12-lead ECG.
- Obtain malaria clinical score.
- Record vital signs.
- Record AEs and use of concomitant medications.
- Review haematology and biochemistry results from Day 7 am collection.
- Randomisation.
- Cannulate participants with an indwelling intravenous (18 or 20 gauge) cannula.
- Collect blood samples for
 - haematology and biochemistry,
 - malaria PCR,
 - parasite *ex vivo* viability,
 - IMP PK (baseline sample),
 - future malaria research sample (if participant consented).

Administer the relevant MMV367 dose under direct observation.

The following procedures will occur after MMV367 administration:

- Follow up participants as in-patients until Day 11 to ensure tolerance of MMV367 and adequate clinical response.
- Perform symptom-directed physical examination if clinically indicated.
- Record vital signs three times a day (at time points specified in Section 1.3) whilst confined.
- Obtain malaria clinical score three times a day (at time points specified in Section 1.3) whilst confined.
- Obtain 12-lead ECG once daily (at time points specified in Section 1.3) while confined.
- Collect blood for haematology and biochemistry at 24 hours post-MMV367 administration.
- Collect blood for malaria PCR following MMV367 administration at 2, 4, 8, 12, 16, 24, 30, 36, 48, 54 and 60 hours (see section 8.1 and 8.2 for time allowed time windows).
- Collect blood samples for IMP PK at 1, 2, 3, 4, 6, 8, 12, 16, 24, 36, 48 and 60 hours post-MMV367 administration (see section 8.1 and 8.2 for time allowed time windows).
- Collect blood for parasite *ex vivo* viability at 8, 16, 24, 36 and 48 hours post-MMV367 administration.
- Record AEs and use of concomitant medications.

The following procedures will occur prior to discharge from the clinical trial unit (Day 11AM):

- Perform symptom-directed physical examination if clinically indicated.
- Obtain a 12-lead ECG.
- Obtain malaria clinical score.
- Record vital signs.
- Collect blood samples at 72 hours post-MMV367 administration for:
 - haematology and biochemistry,
 - malaria PCR,

- IMP PK,
- parasite *ex vivo* viability.
- Record AEs and use of concomitant medications.

12.1.6 OUTPATIENT MONITORING POST-IMP ADMINISTRATION (DAYS 12 TO 27)

Follow up visits will be undertaken on an out-patient basis for clinical evaluation and blood sampling on the scheduled days described below. Follow up visits may occur more frequently if clinically indicated. Follow up visits on Days 17, 20 and 24 are not required if participant has previously been administered definitive antimalarial treatment and returned at least one negative malaria PCR result.

The following procedures will take place on Day 12±4hrs:

- Obtain malaria clinical score.
- Record vital signs.
- Record AEs and use of concomitant medications.
- Check participant diary cards.
- Perform symptom-directed physical examination if clinically indicated.
- Collect blood samples for:
 - malaria PCR,
 - IMP PK,
 - parasite *ex vivo* viability,
 - future malaria research sample (if participant consented).

The following procedures will take place on Day 13±12hrs:

- Obtain malaria clinical score.
- Record vital signs.
- Record AEs and use of concomitant medications.
- Check participant diary cards.
- Perform symptom-directed physical examination if clinically indicated.
- Collect blood samples for:
 - malaria PCR,
 - IMP PK.

The following procedures will take place on Day 15±24hrs:

- Obtain malaria clinical score.
- Record vital signs.
- Record AEs and use of concomitant medications.
- Check participant diary cards.
- Perform symptom-directed physical examination if clinically indicated.
- Collect blood samples for:
 - haematology and biochemistry,
 - malaria PCR,

- IMP PK,
- future malaria research sample (if participant consented).

The following procedures will take place on Day 17±24hrs:

- Obtain malaria clinical score.
- Record vital signs.
- Record AEs and use of concomitant medications.
- Check participant diary cards.
- Perform symptom-directed physical examination if clinically indicated.
- Collect blood samples for:
 - malaria PCR,
 - IMP PK.

The following procedures will take place on Day 20±24hrs:

- Obtain malaria clinical score.
- Record vital signs.
- Record AEs and use of concomitant medications.
- Check participant diary cards.
- Perform symptom-directed physical examination if clinically indicated.
- Collect blood samples for:
 - malaria PCR,
 - IMP PK.

The following procedures will take place on Day 22±24hrs:

- Obtain malaria clinical score.
- Record vital signs.
- Record AEs and use of concomitant medications.
- Check participant diary cards.
- Perform symptom-directed physical examination if clinically indicated.
- Collect blood samples for:
 - haematology and biochemistry,
 - malaria PCR.

12.1.7 DEFINITIVE ANTIMALARIAL TREATMENT

All participants will receive compulsory definitive antimalarial treatment with Riamet® and/or other registered antimalarials if required on Day 24±24hrs, or earlier in the following cases:

- Insufficient parasite clearance following IMP dosing (parasitaemia not reduced ≥ 10 -fold by Day 10 compared with peak parasitaemia on Day 8).
- Parasite regrowth following IMP dosing (initial parasite clearance is followed by asexual parasite regrowth above 5000 parasites/mL).

- Participant discontinuation/withdrawal (see Section 7).
- Investigator's discretion in the interest of participant safety.

The following procedures will be performed prior to antimalarial rescue treatment:

- Obtain malaria clinical score.
- Record vital signs.
- Record AEs and use of concomitant medications.
- Check participant diary cards.
- Perform symptom-directed physical examination if clinically indicated.
- Collect blood samples for:
 - malaria PCR,
 - parasite *ex vivo* viability (only in the event of parasite regrowth),
 - parasite drug resistance (only in the event of parasite regrowth).

12.1.8 END OF STUDY VISIT (DAY 27±24HRS) OR EARLY TERMINATION

The following procedures will be performed at the EOS visit:

- Perform a full physical examination (record body weight).
- Obtain a 12-lead ECG.
- Obtain malaria clinical score.
- Record vital signs.
- Record AEs and use of concomitant medications.
- Collect urine for urinalysis.
- Collect blood samples for:
 - haematology and biochemistry,
 - serum β-hCG pregnancy test for WOCBP,
 - RBC alloantibodies,
 - viral screen,
 - malaria PCR (not required if one negative result previously returned post-definitive antimalarial treatment),
 - safety serum retention sample,
 - future malaria research sample (if participant consented).
- Collect diary card.

If a participant is unwell with detectable parasitaemia or at the Investigator's discretion, the participant may be asked to return to the clinical trial unit after the EOS visit for safety follow up.

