4 STUDY DESIGN

4.1 OVERALL DESIGN

This is an open-label, adaptive study that will utilise the *P. falciparum* induced blood stage malaria (IBSM) model to characterise the pharmacokinetic/pharmacodynamic (PK/PD) profile and safety of MMV367 (the IMP). Up to 18 participants will be enrolled in cohorts of up to 6 participants each. The study will proceed as follows for all participants:

- Screening period of up to 28 days to recruit healthy adult volunteers.
- Day 0: Intravenous inoculation with approximately 2,800 viable *P. falciparum*-infected erythrocytes.
- Days 1-3: Daily follow up via phone call or text message.
- Days 4-7: Daily site visits for clinical evaluation and blood sampling to monitor malaria parasitaemia via quantitative polymerase chain reaction (qPCR).
- Day 7 PM: Start of confinement within the clinical trial unit.
- Day 8: Administration of a single oral dose of the IMP (MMV367). Different doses of MMV367 will be administered across and within cohorts in order to effectively characterise the PK/PD relationship (see Section 4.3 for dose selection rationale).
- Days 8-11: Regular clinical evaluation and blood sampling to monitor malaria parasitaemia and measure MMV367 plasma concentration.
- Day 11 AM: End of confinement within clinical trial unit.
- Days 12-23: Outpatient follow-up for clinical evaluation and blood sampling.
- Day 24: Initiation of compulsory definitive antimalarial treatment with Riamet® (artemether/lumefantrine) and/or other registered antimalarials if required (see section 6.1). Treatment will be initiated earlier than Day 24 in the event of:
 - Insufficient parasite clearance following IMP dosing (parasitaemia not reduced ≥ 10 -fold by Day 10 compared with peak parasitaemia on Day 8).
 - Parasite regrowth following IMP dosing (initial parasite clearance is followed by asexual parasite regrowth above 5000 parasites/mL).
 - Participant discontinuation/withdrawal (see Section 7),
 - Investigator's discretion in the interest of participant safety.
- Day 27: End of study visit for final clinical evaluation and to ensure complete clearance of malaria parasitaemia (at least one negative malaria PCR result required).

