6.1.2 DOSING AND ADMINISTRATION

IMP

A single oral dose of MMV367 will be administered on Day 8 after an overnight fast of ≥ 8 hours. The IMP will be administered as an oral suspension in sterile water. Specific dosing instructions will be documented in the pharmacy manual. Participants will be required to remain fasted for 4 hours after dosing. Different doses of MMV367 will be tested across and within cohorts.

The doses to be tested in Cohort 1 will be as follows:

MMV367 dose	20 mg	90 mg	1500 mg
Number of participants	3	2	1

Specific doses to be tested in subsequent cohorts will be decided by the SDRT based on emerging data during the study (safety, PK, and PD data from preceding cohorts). The maximum dose to be tested in the study will be no more than 1500 mg.

Challenge Agent

The malaria challenge agent, containing an estimated 2,800 viable *P. falciparum* 3D7 parasite-infected erythrocytes in a volume of 2 mL, will be administrated intravenously on Day 0. The actual number of parasites inoculated will take into account the loss of viability resulting from cryopreservation, storage and thawing. Participants will undergo intravenous cannulation. The inoculum will be injected, and the cannula flushed with clinical grade saline. The cannula will then be removed. An extra syringe will be prepared to quantify the parasite count of the challenge agent by PCR.

Definitive antimalarial medications

Compulsory definitive antimalarial treatment for all participants will be initiated on Day 24, if not initiated earlier in accordance with the criteria described in Section 4.1.

Riamet® tablets will be administered as six oral doses of four tablets (total course of 24 tablets equivalent to 480 mg artemether and 2.88 g lumefantrine). The second dose of four tablets will be administered 8±1 h after the first dose. The remaining doses will be administered twice daily (morning and evening).

Malarone® will be utilised as a backup medication to Riamet® in the event of allergy or contraindication to Riamet®. A treatment course consists of four tablets administered daily for three days (total course of 12 tablets equivalent to 3 g atovaquone and 1.2 g proguanil hydrochloride).

Participants may be treated with Primacin® at the Investigator's discretion to ensure clearance of gametocytes. If needed, participants will be administered a single oral dose of six Primacin® tablets (total dose 45 mg primaquine) with food.

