8.3.6 ADVERSE EVENT REPORTING

It is the Investigator's responsibility to document and report all AEs occurring in the clinical trial whether spontaneously reported by the participant, observed by the Investigator (either directly or by laboratory or other assessments), or elicited by general questioning. The period of observation for collection of AEs extends from the time of inoculation with the malaria challenge agent to EOS. These AEs must be recorded on specific AE pages of the eCRF. Events reported prior to this will be recorded as medical history, unless the symptoms worsen during the trial.

The following information should be recorded for all AEs:

- Description
- Dates and times of onset and resolution
- Seriousness (SAE or not)
- AESI (yes/no)
- Severity
 - If severity of an AE changes, only one AE will be reported, with the highest severity recorded in the eCRF and listings and tables. In the clinical file (source data), the description of the AE will report the various severities observed over time.
 - If the AE resolves and then reoccurs, then two AEs will be reported.
- Action taken in response to the AE (including treatment given).
- Outcome.
- Relationship to the trial treatments or procedures (causality assessment), including the IMP, malaria challenge agent, definitive antimalarial medications, or any other treatment or procedure conducted during the trial.

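### No minimum interval separates the Day 24 treatment window from the Day 27 end-of-study window, so a fully compliant end-of-study visit can fall before the last scheduled antimalarial dose

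*Protocol*

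**What the plan says.** **Treatment window.** Protocol 12.1.7 gives all participants "compulsory definitive antimalarial treatment with Riamet® and/or other registered antimalarials if required on Day 24±24hrs", unless an earlier trigger applies. The Schedule of Activities (1.3) puts the Day 24 visit at 384±24 h after the IMP.

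**Final visit.** The heading of 12.1.8 reads "END OF STUDY VISIT (DAY 27±24HRS) OR EARLY TERMINATION", and the Schedule gives 456±24 h. Section 4.1 describes Day 27 as "End of study visit for final clinical evaluation and to ensure complete clearance of malaria parasitaemia".

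**Course.** Section 6.1.2: "Riamet® tablets will be administered as six oral doses of four tablets" and "The second dose of four tablets will be administered 8±1 h after the first dose". The other four doses follow morning and evening. Malarone, the backup, is one dose a day for three days. Under 6.4 only the first dose must be observed in clinic; the rest may be taken at home, with a call or text to check compliance.

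**What ends at EOS.** Section 8.3.6: "The period of observation for collection of AEs extends from the time of inoculation with the malaria challenge agent to EOS". Take-home doses are recorded on the diary card (8.2.6), which is collected at EOS (12.1.8). Concomitant medication recording also stops there (6.5).

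**PCR.** Section 8.1.2 lets sampling stop after one negative result following definitive treatment. Section 12.1.8 waives the EOS sample if a negative has already been returned post-treatment. Footnote d to the Schedule asks only that treatment has been administered and a negative returned.

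**The concern.** Both windows are measured from the IMP dose rather than from each other or from the participant's first antimalarial dose. A late treatment start and an early EOS can therefore occur in the same participant with no deviation, and the time between them can be shorter than the course.

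For a participant treated at the Day 24 visit, no further visit is scheduled before EOS, and the Day 24 PCR is drawn before treatment begins (12.1.7). The EOS sample is thus the only scheduled post-treatment clearance test. If EOS comes mid-course, the doses still to be taken at home fall after the diary has been handed in, and any AE that starts afterwards falls outside the collection period. The SAP uses these data: section 9 summarises exposure to the rescue medications, and 11.3.1.1 lists each AE's relationship to them.

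**Working it through.** **Reproducing the plan's hours.** With the IMP on Day 8, nominal hour = (study day − 8) × 24.
- Day 24: 16 × 24 = 384 h. Day 27: 19 × 24 = 456 h. Both match the Schedule.

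**Window edges.**
- Treatment start: 384 − 24 = 360 h to 384 + 24 = 408 h.
- EOS: 456 − 24 = 432 h to 456 + 24 = 480 h.

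**Gap from first antimalarial dose to EOS.**
- Nominal: 456 − 384 = 72 h.
- Minimum: 432 − 408 = 24 h.
- On-time start, earliest EOS: 432 − 384 = 48 h.
- Maximum: 480 − 360 = 120 h.

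**Time of the last dose.** The protocol does not state this, so it is derived from 6.1.2. For the first and third rows I assume morning and evening doses at 08:00 and 20:00, with the third dose on the morning after the start.

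| Assumption | Riamet dose times (h) | Last dose |
|---|---|---|
| First dose 08:00 | 0, 8, 24, 36, 48, 60 | 60 h |
| Strict 12 h spacing after dose 2 | 0, 8, 20, 32, 44, 56 | 56 h |
| First dose 16:00 | 0, 8, 16, 28, 40, 52 | 52 h |

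The ±1 h on the second dose does not move the last one under the fixed clock times. Malarone is taken at about 0, 24 and 48 h.

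**Comparison.**
- At 72 h, all doses are complete; EOS is 72 − 60 = 12 h to 72 − 52 = 20 h after the last Riamet dose.
- At 48 h, 4 to 5 of 6 Riamet doses have been taken; the last Malarone dose falls at about the same time as EOS.
- At 24 h, 2 to 3 of 6 Riamet doses, or 1 to 2 of 3 Malarone doses, have been taken.
- EOS precedes the last Riamet dose once the two visits together drift towards each other by more than 12 h (60 h course) or 20 h (52 h course).

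**Who is outside this.** Someone treated at the Day 22 visit starts no later than 336 + 24 = 360 h, which leaves at least 432 − 360 = 72 h before EOS. The problem is confined to treatment at the Day 24 visit.

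**Room in the existing window.** Latest start plus longest derived course: 408 + 60 = 468 h, which is inside the 480 h limit.

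**The case against.** The strongest reply is that the schedule as planned works. At nominal timing EOS follows the last dose, and the 24 h figure needs the latest start and the earliest EOS in the same participant. That is right, and it limits the point to visits that drift together. It does not remove it: an on-time start with EOS at its early edge already puts EOS before the last Riamet dose across the whole 52 to 60 h range.

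Safeguards exist as well. Compliance calls or texts have no stated end at EOS (6.4). A return visit is possible at the investigator's discretion (12.1.8). AEs open at the last visit continue to be followed (8.3.5). Inclusion criterion 1 requires availability for up to two weeks after EOS. These reduce the exposure, and calls may pick up some information. None of them schedules a later PCR, a later diary collection or collection of new-onset AEs.

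A reader might also infer four stronger things that the documents do not support:
- *That a mid-course negative PCR clearly ends follow-up.* Sections 8.1.2 and 12.1.8 can be read as meaning after the full course, while footnote d is looser. The text is ambiguous. Under the stricter reading a mid-course EOS sample would not count, and no later visit is scheduled to replace it.
- *That the window makes the test uninformative for participants already cleared by MMV367.* A negative in such a person says little about the antimalarial course on any date, including after the last dose.
- *That every participant treated on Day 24 is affected.* Only those whose visits converge are.
- *That the window is what makes EOS ECG and laboratory values differ in time since treatment.* Participants treated earlier for regrowth already differ in this way.

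**Conclusion.** The point holds in a limited form. The permitted minimum of 24 h, and 48 h after an on-time start, follows exactly from the Schedule; no section sets a minimum interval. The 52 to 60 h course length rests on the dosing text and the assumed clock times, and the conclusion is the same throughout that range. For participants treated at the Day 24 visit whose visits drift together, EOS can precede the last scheduled dose with no deviation, and take-home doses and new AEs after it have no planned capture.

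The consequence lies in safety follow-up and treatment-exposure data. A reader might infer damage to the main analyses, but the documents show none: post-rescue parasite data are flagged to be ignored in the PK/PD dataset (SAP 10.3.1), the clearance regression stops at the first all-negative time point or three time points after the minimum (SAP 11.1.2), and the last PK sample is on Day 20. How many participants would be affected cannot be calculated, because the documents do not show how often sites would use the window edges and doses after Cohort 1 are undecided. This is a correction worth making, not a flaw that threatens the trial.

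**What to change.** The sponsor should reconcile the windows in Protocol 1.3, 12.1.7 and 12.1.8 with the course length implied by 6.1.2, so that the EOS assessments, diary collection and AE cut-off cannot precede the last scheduled dose. It should also make the PCR wording in 8.1.2, footnote d to the Schedule and 12.1.8 consistent on whether a negative result taken before the course is complete counts. The matching Schedule in SAP 3.3 would follow. How this is done is for the sponsor; no treatment regimen or clinical rule is proposed here.

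The cost is wording and some scheduling flexibility. With a 60 h course, the earliest EOS would move from 432 h to 384 + 60 = 444 h after an on-time start (12 h), and to 468 h after the latest permitted start (36 h). After the earliest start it would not move (360 + 60 = 420 h). All of these fit within the existing 480 h limit, so no visit is added.
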